1.0 Study Summary

Study Title	Long-term Effects and Safety of DHA Supplementation in Toddlerhood for Children born Preterm
Study Design	The present follow up study involves a prospective cohort of toddlers born preterm from our previous randomized, double-blind, placebo-controlled Omega Tots trial (ClinicalTrials.gov Identifier: NCT01576783, IRB11-00343, IRB14-00342).
Primary Objective	The primary objective for this study is to determine the long-term effect of daily dietary supplementation at age 1 year with omega-3 docosahexaenoic acid (DHA) and omega-6 arachidonic acid for children born preterm by comparing general cognitive ability, language, and multiple facets of executive function between the intervention and placebo arms at ages 8½ - 10 ½ years.
Secondary Objective(s)	The secondary objective of this study is to determine the role of variability in fatty acid metabolism genetics en masse on the effect of supplementation on short and long-term outcomes, and further focus on 2 previously published FADS2 genetic variants.
Research Intervention(s)/ Investigational Agent(s)	Children from the original Omega Tots trial (NCT01576783) were previously randomized to 180 days of DHA+AA (200mg DHA+200mg AA daily) or placebo (400mg corn oil), dissolving powders in blinded foil packets. At this time, participants will not receive any further intervention or investigational agents. Long-term outcomes will be observed and recorded accordingly across intervention groups
IND/IDE #	112885
Study Population	Participants will be the 377 parent-child dyads from the original Omega Tots trial. They were born at <35 weeks' gestation, were 10-16 months of age (age corrected for prematurity) at trial enrollment, and had been patients at Nationwide Children's Hospital NICU or Follow-up clinic.
Sample Size	All 377 randomized children from the original Omega Tots trial (NCT01576783) will be eligible for in-person follow-up at age 8½ - 10 ½ years.
Study Duration for individual participants	Participants will partake in one comprehensive study visit when children are sometime between 8 years, 180 days and 10 years, 180days of age. It is expected that participant enrollment will begin by September 1, 2020, and that human subjects' activity will be completed by February 1, 2025.

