4.0 Study Endpoints

4.1 Describe the primary and secondary study endpoints.

Primary outcomes (child) - General cognitive ability, language, and executive function.

- General cognitive ability - We will use the *DAS-II General Conceptual Ability (GCA)* standard score as our primary measure for general cognitive ability.
- Language - We recognize that language is a major component of cognitive ability, but given the specific effects on language we observed in the original trial and the striking deficits in language caused by prematurity, we have elected to specifically focus on language as a separate primary outcome and examine it in more depth than the *DAS-II* can. Thus, we will use the *Clinical Evaluation of Language Fundamentals-5th ed (CELF-5)(core subtests)* as our measure for language. We will use the *Core Language standard score* as our primary measure of language.
- Executive function - Our primary EF measure will be an executive function factor derived from the following NIH Toolbox tasks: *Dimensional Change Card Sort, Flanker, and Pattern Comparison tests*.

Secondary outcomes and measures.

We propose a handful of secondary outcomes and measures to accompany our primary measures shown above. These serve 3 purposes. 1) Some are additional measures of the primary outcomes but rely on a different reporter. 2) Some were chosen because they compensate for small shortcomings in the Toolbox, and so they ensure we measure the 3 key aspects of EF (inhibition switching, working memory). These will be part of sensitivity analyses compared to the Toolbox. 3) Academic achievement will be measured because it will reveal how identified cognitive deficits manifest in academic skills particularly important in middle childhood.

Secondary outcomes - Child activities
Grooved Pegboard Task
Wechsler Intelligence Scales for Children-V (digit span, picture span)
Kaufman Test of Educational Achievement-3 (Letter and Word Recognition, Math Computation, Object Naming Facility and Associative Fluency subtests)
Weight, height and BMI for age z-scores (WHO standards), percent body fat
NIH Toolbox Friendship (Ages 8-17) Fixed Form
Secondary outcomes - Caregiver report (teachers will complete instruments with *)
Behavior Rating Inventory of Executive Function 2nd ed. *

PROTOCOL TITLE: Long-term Effects and Safety of DHA+AA Supplementation in Toddlerhood for Children born Preterm

Teacher Report Form 6-18 (Syndrome & DSM-Oriented subscales)*

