6.2 Study measures: Direct assessment of child

Child testing will include the following measures. All assessments will be administered or coordinated by trained staff. The order that measures are administered may change slightly based on child’s engagement, time constraints, or other factors.

- a) *Differential Ability Scales-II General Conceptual Ability assessment.* This instrument can assess and identify children’s cognitive strengths and weaknesses that are important to learning by utilizing various stimulus books and manipulatives (i.e.: blocks). Assessment time is approximately 50 minutes.
- b) *Clinical evaluation of Language Fundamentals, 5th edition core tests.* This is a comprehensive instrument has a total of 16 subtests that can assess children’s written and oral language skills, as well as their reading comprehension. Assessment time is approximately 30 minutes.
- c) *NIH Toolbox Cognition Battery.* Total assessment time is approximately 20 minutes. The NIH Toolbox is a multidimensional set of brief measures assessing cognitive function for participants aged 3 – 85 years. *The Flanker, Dimensional Card Sort, and Pattern Comparison subtests* are part of the child Cognition Battery that assesses executive function, cognitive flexibility, attention, episodic memory, processing speed, and working memory.
- d) *Kaufman Test of Educational Achievement-3 (Math Computation, Letter and Word Recognition, Object Naming Facility and Associative Fluency).* This brief assessment can produce composite scores that measure children’s reading, math, and written language skills. Assessment time is approximately 20 minutes.
- e) *A Grooved Pegboard Task and Edinburgh Handedness Inventory-Short Form.* This brief task requires children inserting pegs inside a board. The handedness form is a 4-item measure that assesses the child’s handedness. Child are verbally asked which hand they prefer to use for 4 tasks. It takes approximately 5 minutes to complete these activities.
- f) *The Wechsler Intelligence Scales for Children-V digit span, and the Wechsler Intelligence Scales for Children-V picture span* are brief cognitive assessment that measure working memory. Assessment time is approximately 15 minutes.
- g) Peer Relationships are assessed using the *NIH Toolbox Friendship (Ages 8-17) Fixed Form.* This 5-item measure assesses quality of relationships with friends and other

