Analyses for Aim 1 will follow intent to treat principles, the most rigorous approach to RCT data. By using intent to treat we are able to detect lasting effects of DHA+AA supplementation if they are present at the magnitude we anticipate. Children who were randomized but discontinued taking treatment or were lost to follow-up will be included in analyses. Our main goal will be to estimate the effect of treatment assignment on our 3 primary outcomes at age 8½ - 10 ½ (DAS-II GCA, CELF-5 language, Toolbox EF) using the following mixed model, consistent with the analysis of our Omega Tots trial: $y_{it} = \beta_0 + \beta_1 Time_t + \beta_2 Time_t \times Trt_i + \epsilon_{it}$, where implicitly it is assumed that there is no main effect of Trt_i , y_{it} is the outcome of interest at time t , $Time_t$ is coded as 0 for the outcome at baseline (i.e., the covariate for our purposes here) and 1 for the post-randomization measure of the outcome obtained at age 8 ½ - 10 ½, and the primary effect of interest is β_2 , which corresponds to the difference between groups on the outcome at age 8 ½ - 10 ½. In this model, the baseline measure of the outcome is constrained to have equal means across groups by assuming there is no main effect of the intervention, Trt_i . This constraint yields a statistical test for β_2 analogous to the test of the treatment group main effect via ANCOVA controlling for the baseline measure without requiring list-wise deletion due to missing data. Specifically, our model is estimated using maximum likelihood estimation, and therefore allows for outcome data at either time point to be missing at random. We will account for clustering due to twins/triplets in our sample by adding a random effect at the family level. Exploratory pre-specified sub-group analyses will proceed by testing interaction terms added to the models for sex, birthweight (<1500g vs ≥ 1500 g), socioeconomic (household income dichotomized at the median), and daily dietary intake of DHA plus EPA (below vs above the median).

PROTOCOL TITLE: Long-term Effects and Safety of DHA+AA Supplementation in Toddlerhood for Children born Preterm

Interactions with $p < .20$ will be considered statistically significant, and stratified results will be reported consequently. Analyses will use the MIXED procedure, SAS 9.4.

Statistical power, sample size, and analysis for Aim 2 (i.e. genetic biospecimens):

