To address the first part of Aim 2, we apply the standard method for estimating SNP-based heritability, which assumes the common SNP effect is a random effect in a mixed linear model and with variance decomposed into variance components for genetic and non-genetic effects. The generic model is therefore specified as: $y = \beta_0 + X\beta + g + \epsilon$, where g is the random genetic effect and further the model is constrained by $V = A\sigma_g^2 + I\sigma_e^2$ where V is the overall variance decomposed into genetic and non-genetic (i.e. environmental) components; the matrix A is the genetic relationship matrix, which is similar to the concept of a distance matrix in geospatial modeling, though in this case the distance is genetic similarity calculated from the genome-wide SNP data. Therefore, genetic effects are associated with the covariance matrix for common SNPs (called A) and non-genetic effects with the identity matrix (called I). Using the identity matrix for this purpose assumes no shared environment effects, which is valid since only unrelated persons are included in the calculation. We routinely assess age, sex, and socioeconomic status as covariates, and always include ancestry principal components. SNP-based heritability can be performed on case-control datasets, population cohorts or other collections of unrelated individuals. Thus, while traditional heritability assumes zero genetic covariance between “unrelated” persons, observed SNP-based genetic covariance will rarely if ever be zero. The cohort includes mostly unrelated individuals (55 sets of twins/triplets). Rather than model the relationships among related individuals and lose power from increased degrees of freedom, we will apply a resampling procedure. Sampled datasets with 1 twin chosen at random ensures the datasets in each replicate contain only unrelated persons but the average over the sampled datasets converges on estimates that use information from all children. In our cohort we will have $>80\%$ power to detect SNP-based heritabilities as low as 21%, after accounting for the resampling procedure. While fatty acid markers have not explicitly been tested this way before, the relationship between genetics and many metabolism biomarkers in blood is much higher than a heritability of 21%, giving further reassurance that the study is adequately powered. The test of *en masse* SNP effects in the context of this clinical trial takes the form similar to Aim 1, $y_{it} = \beta_0 + \beta_1 Time_{it} + \beta_2 Trt_{it} + \beta_3 g + \beta_4 Trtxg + \beta_5 Timexg + \beta_6 Time_i Trt_i + \beta_7 Time_i x Trtxg_i + \epsilon_{it}$, while the constraints on V are still imposed. The matrix A will be estimated using the software GCTA and the model will be tested using R or Python depending on whether numerical issues arise in the numerical matrix calculations. We can perform this model using structural equation models implemented in the R library genomicSEM. This modeling platform will allow us to use *en masse* SNPs in the models described above.

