
To address the second part of Aim 2, our primary tests will be conducted using 2 linear mixed models similar to that described above in Aim 1. We will estimate the effect of treatment assignment on our 3 primary outcomes at age 8 ½ - 10 ½ (DAS-II GCA, CELF-5 language, Toolbox EF) except that the interaction of treatment by time will include one SNP at a time. These two genetic variants come from the two previously identified SNPs in the literature that we selected as the primary SNPs of interest for this study (SNPs rs1535, rs174575 in the *FADS2* gene). We will be conducting a test of null hypothesis that each SNP has no interaction affecting the outcome. Using the model terminology from Aim 1, $y_{it} = \beta_0 + \beta_1 Time_{it} + \beta_2 Trt_{it} + \beta_3 SNP_i + \beta_4 TrtxSNP_i + \beta_5 TimexSNP_i + \beta_6 Time_i Trt_i + \beta_7 Time_i x TrtxSNP_i + \epsilon_{it}$, where SNP_i is defined as two groups based on the presence/absence of the rare allele at that locus. Last, although we will make efforts to have DNA from every child, some parents may refuse or sample quality could

PROTOCOL TITLE: Long-term Effects and Safety of DHA+AA Supplementation in Toddlerhood for Children born Preterm

occasionally be compromised. We will treat missing genetic data just as for other missing data (see Aim 1 – Statistical Analysis).

Analysis plan for secondary outcomes:

Secondary outcomes will be analyzed as for the plan listed above for Aim 1, with the exception that binary outcomes will use logistic or log-binomial models. Secondary outcomes have been specified under section 4.0 Study Endpoints. Results will not be adjusted for multiple comparisons because of the pitfalls of that approach (see Rothman, Epidemiology 1990).

Exploratory analysis of genetic data:

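### The FADS2 equation frees baseline treatment terms that the Aim 1 model fixes at zero, so its three-way test is a generally less precise change-score contrast

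*Combined protocol and SAP*

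**What the plan says.** Section 17.1, statistical analysis for Aim 1, fits baseline and follow-up jointly, with Time coded 0 and 1 and no treatment main effect. The reason is given: "the baseline measure of the outcome is constrained to have equal means across groups by assuming there is no main effect of the intervention". The plan presents the resulting test as the counterpart of ANCOVA, without losing children who have one missing value. The only random effect it states is this: "We will account for clustering due to twins/triplets in our sample by adding a random effect at the family level".

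For the two FADS2 variants, the same section says "our primary tests will be conducted using 2 linear mixed models similar to that described above in Aim 1", "except that the interaction of treatment by time will include one SNP at a time". The equation that follows has eight mean terms: intercept, Time, Trt, SNP, Trt-by-SNP, Time-by-SNP, Time-by-Trt and Time-by-Trt-by-SNP. Two of these, Trt (β2) and Trt-by-SNP (β4), are baseline treatment contrasts under the 0/1 time coding. The text does not say why they are there, and it does not name the coefficient to be tested. The en masse SNP model, which "in the context of this clinical trial takes the form similar to Aim 1", carries the corresponding extra terms.

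**The concern.** The prose says the FADS2 models are the Aim 1 model with a SNP brought into the treatment-by-time interaction. The equation is a different model. Genotype is fixed before randomisation, so among randomised children both the baseline arm difference and the baseline arm-by-genotype difference are zero in expectation. Estimating them gives up precision that Aim 1 deliberately keeps.

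With both terms free, Time-by-Trt-by-SNP (β7) becomes a difference in change from baseline, so its precision depends on how the baseline measure is scaled relative to the follow-up measure. For executive function the two cannot be the same instrument. The Toolbox comprises "brief measures assessing cognitive function for participants aged 3" years and upwards, whereas the children "were 10-16 months of age (age corrected for prematurity) at trial enrollment". The scale of the follow-up score is also unstated: "Our primary EF measure will be an executive function factor derived from the following NIH Toolbox tasks". The relative SD therefore stays open until an analyst chooses a scaling.

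At stake is efficiency, not bias, on an interaction test with little power to spare.

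**Working it through.** **The plan's own figure.** No power is stated for the FADS2 tests. The nearest figure is Aim 1: 300 children, 0.32 SD, α = 0.05 (taken as two-sided). Φ(0.32/√(2/150) − 1.96) = Φ(0.811) = 79.1%, and the exact detectable difference is 0.3235 SD. The stated figure is reproduced to rounding.

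**What β7 estimates.** Eight mean parameters for eight arm × carrier × time cells make the model saturated. With complete pairs, β7 equals the difference-in-differences of mean change scores; on one simulated data set both were 0.37449. The time subscript on Trt does not alter this. If Trt were zero at baseline, β2 would duplicate Time-by-Trt and β4 would duplicate β7, and the model would not be identified.

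**Inputs**
- From the plan: 377 randomised, 300 expected at follow-up, stored blood for about half the cohort (section 7.0).
- Assumed: ρ 0.2–0.4; k from ρ to 1; 300 genotyped follow-ups (n_c); unstructured within-child covariance; twin clustering ignored.
- Genotyped baselines (n_0), assumed: 300 (complete pairs); 338 (adds half of the 77 non-attenders, if stored blood is as common among them); 377 (upper bound).

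**Variance.** With follow-up SD 1, the per-cell variance is (1 − ρ²)/n_c with the two terms removed, and (1 − ρ²)/n_c + (ρ − k)²/n_0 as printed. The ratio is

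1 + (n_c/n_0)(ρ − k)²/(1 − ρ²),

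which agrees with the full information matrices of the 8-term and 6-term models. Example: ρ = 0.3, k = 1, n_0 = 300 gives 1 + 0.49/0.91 = 1.538.

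| k | n_0 | ρ = 0.2 | ρ = 0.3 | ρ = 0.4 |
|---|---|---|---|---|
| ρ | any | 1.000 | 1.000 | 1.000 |
| 0.5 | 300 | 1.094 | 1.044 | 1.012 |
| 0.5 | 338 | 1.083 | 1.039 | 1.011 |
| 0.5 | 377 | 1.075 | 1.035 | 1.009 |
| 1 | 300 | 1.667 | 1.538 | 1.429 |
| 1 | 338 | 1.592 | 1.478 | 1.380 |
| 1 | 377 | 1.531 | 1.428 | 1.341 |

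At ρ = 0.3 and k = 1 the printed test carries the information of 300/1.538 = 195 to 300/1.428 = 210 children. The loss is larger still if k exceeds 1.

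**If β4 + β7 is tested instead.** The ratio is 1 + (n_c/n_0)ρ²/(1 − ρ²), whatever k is: 1.04–1.19 with n_0 = 300 and 1.03–1.15 with n_0 = 377.

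**Detectable interaction (80% power, ρ = 0.3).** With 50% carriers (assumed) there are 75 children per cell. Constrained: 2.80 × √(0.91 × 4/75) = 0.62 SD. Printed: 0.63 SD at k = 0.5. At k = 1 it is 0.617 × √1.428 = 0.74 to 0.617 × √1.538 = 0.77 SD. With 30% carriers and k = 1, 2.80 × √(0.91 × 2 × (1/45 + 1/105)) = 0.673 SD constrained, against 0.673 × √1.428 = 0.80 to 0.673 × √1.538 = 0.84 SD printed.

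**Simulation (300 complete pairs).** At ρ = 0.3, k = 1, the empirical SD of the interaction estimate was 0.271 printed and 0.217 ANCOVA. Power for a true 0.6 SD interaction was 58% and 77% (analytic 59% and 78%). Rescaling only the baseline in one data set moved the printed t from 3.87 (k = 0.3) to 2.50 (k = 1); ANCOVA stayed at 3.83.

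**Removing the terms without fixing the covariance.** For singletons, a family random effect plus residual implies one common variance at both times. Let v = (1 + k²)/2 and w = ρk/v. For complete pairs the constrained contrast then has true variance 1 + w²k² − 2wρk but model-based variance v(1 − w²). At ρ = 0.4, k = 0.5: v = 0.625, w = 0.32, true variance 0.898, model-based 0.561. The printed equation gives 0.850 and the unstructured or ANCOVA form 0.840. Type I error is 2·P(Z > 1.96√(0.561/0.898)) = 12.1% (simulated 12.2%). It is 8% at k = 0.75 and 5% at k = 1.

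**The case against.** Several points on the other side have weight.

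- **The tested coefficient is inferred.** The text speaks of outcomes at age 8½–10½, which in the printed equation would be β4 + β7. On that reading the loss is only 3–19%. This stands as a limit on the size; the unnamed coefficient is itself a gap to close.
- **The large losses need k near 1.** The documents name neither a baseline instrument nor an SD. k = 1 is natural if both scores are standardised, but at k = 0.5 the loss is under 10%. This stands, and is why a range is given.
- **The constrained model is better only with a suitable covariance.** Under a common variance the printed contrast can be the more precise, and it keeps its type I error where the constrained fit does not. This is correct, so the fix must have two parts.
- **Free baseline terms are defensible in a genotyped subset.** Some genotypes depend on saliva collected at follow-up, so balance in that subset is not guaranteed by randomisation. This justifies keeping the printed model as a sensitivity analysis. The plan does not give it as a reason.
- **Practical effect is limited.** This is a secondary objective. For a 0.3 SD interaction at ρ = 0.3, k = 1 and 50% carriers with complete pairs, power is about 27% constrained and 19% printed, inadequate either way.

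None of this explains why the equation departs from the model it is said to follow.

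**Conclusion.** The concern holds. The FADS2 equation abandons the Aim 1 baseline constraint without explanation. With complete pairs its three-way coefficient is exactly a change-score contrast; with additional baseline-only children it still targets the difference in change. Given a correct within-child covariance, it is never more precise than the constrained form and equals it only at k = ρ.

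The inconsistency is certain. The size is conditional on ρ, k and the number of genotyped baselines, none of which the documents give, and ranges from nothing to about two-thirds extra variance over the values examined. There is no bias under randomisation. The change is worth making because it applies the plan's own Aim 1 principle and removes dependence on an unstated scaling choice. Confidence in the practical size is medium. The loss in the en masse model, where the genetic effect is random, was not quantified.

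**What to change.** Make two changes together in the FADS2 part of section 17.1:

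1. Remove Trt and Trt-by-SNP from the equation, keeping SNP, Time, Time-by-SNP, Time-by-Trt and Time-by-Trt-by-SNP.
2. Specify an unstructured covariance for each child's baseline and follow-up values, alongside the family random effect.

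Alternatively, use ANCOVA on the age 8½–10½ score with Trt, SNP, Trt-by-SNP and the baseline measure. This loses children without a baseline value.

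Name the tested coefficient: Time-by-Trt-by-SNP, or Trt-by-SNP in the ANCOVA. Report the printed eight-term model as a sensitivity analysis, because the zero-baseline constraint assumes that having a genotype does not depend jointly on arm and baseline score. Align the en masse equation or justify its difference. Two minor clarifications: whether the ancestry components enter the FADS2 models, and that a missing genotype means a complete-genotype analysis.

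The cost is SAP wording and minor programming, with no new data.
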